## Statistical Analysis Plan (Twitter and Cardiovascular Health: Twitter and Hypertension)

We will use summary statistics to compare demographics and survey responses (health status, ideal CV health status, self-practices perceived usefulness/ease of use) between groups. Categorical variables will be presented as frequencies and percentages and continuous baseline variables will be presented as means and standard deviations (if skewed these will be presented as medians and interquartile ranges).

Our primary outcome will be a 5mmHg change in systolic blood pressure from baseline to study end at 6 months. We will conduct an intent-to-treat analysis. We will use paired t-tests to compare the mean difference in SBP between the intervention and control groups. We will also conduct a multiple linear regression analysis for change in SBP adjusting for covariates which may be imbalanced even after randomization to improve efficiency of our estimates. We will also adjust for baseline SBP. The distribution of change in SBP will be assessed and if it is non-normal (skewed) we will use an appropriate transformation (such as natural log) or we will use a generalized linear model with appropriate family and link choices to model our outcome. For the secondary outcome measure, we will use paired t-test for pre-post differences of PAM scores. A multiple linear regression model will also be used to account for additional imbalances in demographic and baseline health characteristics not evenly distributed by arm. In all models, a binary indicator for control/intervention group will be included. Baseline PAM score will also be adjusted for in the model. Covariates with missing data will be assessed for patterns of missingness and non-ignorability and will be multiply imputed if deemed necessary and reasonable.

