Survey compensation of a gift card worth \$25 would be provided for completion of the final survey at 6 months. Baseline and follow-up surveys will include questions regarding patient activation (PAM-13), self-rated health (SF-1), ideal CV health (BRFSS), HTN self-care practices and demographics. To assess technology use, we will also ask questions from the *Perceived usefulness*, and *Perceived ease of use* surveys. Patients will also consent to having their electronic health records accessed to validate clinical data (e.g. blood pressure (BP), BMI).

Control: The control group study participation would include completing a baseline survey and a survey 6 months later.

Intervention: Participants randomized to the intervention group will be asked to follow the study Twitter account, tweet or retweet health content twice per week using #health and complete a survey at study initiation and 6 months later. Participants will be sent weekly reminders to tweet.

Outcome measures: The primary outcome measure will be change in systolic blood pressure (5mm). The secondary outcome will be patient activation measured by the PAM (a measure of behavior change that has been shown to be changeable over time). Baseline variables will include demographic variables (gender, age, race/ethnicity, and geographic region of residence).

Sample size: Sample size estimates based on the ability to detect a 5mmHg difference in systolic blood pressure at 90% power and type I error of 0.05. We planned to enroll approximately 240 in each control and intervention group, for a total of 480 participants, accounting for a 35% lost to follow up for an online Twitter intervention (total up to 648).

Data analysis: We will use summary statistics to compare demographics and survey responses (health status, ideal CV health status, self-practices perceived usefulness/ease of use) between groups. Categorical variables will be presented as frequencies and percentages and continuous baseline variables will be presented as means and standard deviations (if skewed these will be presented as medians and interquartile ranges).

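### Beyond the fixed baseline SBP and PAM scores, covariates are chosen by chance imbalance, which forgoes some precision for SBP and leaves both models unsettled until the arms are compared

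*SAP*

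**What the plan says.** The SAP and the Protocol's data analysis text give the same plan. After a t-test for SBP, the SAP adds a regression: "We will also conduct a multiple linear regression analysis for change in SBP". The criterion for the covariates, and the reason for including them, read: "adjusting for covariates which may be imbalanced even after randomization to improve efficiency of our estimates". It then fixes one covariate: "We will also adjust for baseline SBP".

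For PAM, a regression is used "to account for additional imbalances in demographic and baseline health characteristics not evenly distributed by arm", and again one covariate is fixed: "Baseline PAM score will also be adjusted for in the model". No efficiency aim is given for PAM.

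Neither document names the further covariates, says what counts as imbalanced, or asks that a covariate predict the outcome. The Protocol's outcome measures paragraph states "Baseline variables will include demographic variables (gender, age, race/ethnicity, and geographic region of residence", but does not assign these variables to a model.

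**The concern.** In a randomised comparison, adjustment gains precision from covariates that predict the outcome. Observed imbalance is chance and carries no information about prediction. A rule based on imbalance therefore leaves out a prognostic covariate that happens to be balanced and admits an irrelevant one that happens not to be. For SBP, where efficiency is the stated reason for adjusting, the criterion and its purpose do not match.

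The second issue applies to both models. With no list and no threshold, the model can be written down only once the arms have been compared at baseline, and several different models would comply. At stake are some precision for SBP and, for both outcomes, confidence that the reported model was not chosen for its result.

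**Working it through.** **Inputs from the documents.** Protocol, sample size paragraph: 240 per arm, 90% power, type I error 0.05, and "the ability to detect a 5mmHg difference in systolic blood pressure". Sidedness is not stated; two-sided is assumed. No SD, correlation or R-squared is given.

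**The plan's own figure.** Without an SD, 240 per arm cannot be reproduced directly. Solving for the SD: 5 / [(1.960 + 1.282) × √(2/240)] = 16.9 mmHg (18.7 if one-sided). An SD of 17 returns 243 per arm, so 17 is used below, with 240 per arm analysed.

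**What the rule selects.** Assume 8 candidates, 2 of them prognostic, and imbalance defined as p<0.10. The expected number selected is 8 × 0.10 = 0.8. The chance that at least one prognostic covariate enters is 1 − 0.9² = 19%. Simulation (4,000 trials per scenario) gave about 0.8 and 18-20%.

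**What a fixed list could gain.** With correlation r between baseline SBP and change, and a share R² of the residual variance explained by the list:

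SE = 17 × √(2/240) × √(1 − r²) × √(1 − R²); power ≈ Φ(5/SE − 1.96).

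Taking r = 0.4, the middle of an assumed 0.3 to 0.5:

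| Model | SE | Power |
|---|---|---|
| Unadjusted | 1.55 | about 90% |
| Baseline SBP only | 1.42 | 94.0% |
| List, R² 2% | 1.41 | 94.4% |
| List, R² 5% | 1.39 | 95.0% |
| List, R² 10% | 1.35 | 96.0% |
| List, R² 20% | 1.27 | 97.6% |

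**What the rule delivers.** A simulation with baseline SBP in the model gave these mean reported SEs:

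| R² | Baseline SBP only | Imbalance rule | Fixed prognostic list |
|---|---|---|---|
| 10% | 1.41 | 1.41 | 1.35 |
| 20% | 1.42 | 1.41 | 1.27 |

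Putting 1.41 in the power formula gives 94.4%, against 95.9% for 1.35 and 97.6% for 1.27: gains of about 1.5 and 3 points. A list that was half non-prognostic gave nearly the same SE as a fully prognostic one.

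A second simulation (2 prognostic and 6 other candidates, true effect 5 mmHg) set R² as a share of the total variance of change. Dividing by 1 − r² gives the residual share:

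| r | R² of total (of residual) | Baseline only: SE, power | Rule: SE, power | List: SE, power |
|---|---|---|---|---|
| 0.3 | 0.05 (5.5%) | 1.481, 0.919 | 1.483, 0.918 | 1.443, 0.932 |
| 0.3 | 0.20 (22%) | 1.481, 0.921 | 1.470, 0.931 | 1.311, 0.968 |
| 0.5 | 0.05 (6.7%) | 1.345, 0.960 | 1.346, 0.962 | 1.302, 0.969 |
| 0.5 | 0.20 (27%) | 1.344, 0.959 | 1.330, 0.965 | 1.154, 0.990 |

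List minus rule is about 1 point in the low-R² rows and 2.5 to 3.7 points in the high-R² rows, whose residual shares are a little above 20%.

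**Type I error.** In the same four scenarios with no effect, the rule rejected in 0.051, 0.045, 0.043 and 0.042 of trials; baseline-only rejected in 0.054, 0.053, 0.046 and 0.054. The Monte Carlo standard error is √(0.05 × 0.95 / 4000) = 0.003. The rule removes chance imbalance in just those trials where it is large, so the estimate varies less than its reported SE suggests (1.284 against 1.331 at r = 0.5, R² = 0.20).

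**The case against.** The strongest reply is that little is lost. The fixed baseline value is usually the strongest single predictor, so most of the available efficiency is kept. A reader might infer that the models lose the efficiency the plan claims. The documents do not support that: baseline SBP enters whatever its balance, the rule was never materially less precise than baseline-only in the simulations, and efficiency is claimed for SBP alone. This part of the reply stands. So does the point that an irrelevant imbalanced covariate costs little: one degree of freedom and roughly 1% of variance at this sample size.

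The benefit of a fixed list also depends on covariates that truly predict SBP change beyond baseline SBP. The documents do not show that age, gender, race/ethnicity or BMI do so. That too stands, and is why the 2-5% rows belong in the table.

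A reader might also infer an inflated error rate. Reporting the most favourable of five compliant models (unadjusted, three imbalance thresholds, all covariates) gave about 7-8% in simulation. But the five versions are invented for illustration, and the plan nowhere proposes reporting the best one. The regression is also additional to a t-test that needs no covariate choice, although the text does not say which of the two is primary.

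Finally, since the SBP sentence does not say baseline, it could be read as admitting follow-up survey items. The natural reading is chance imbalance in baseline characteristics, and the Protocol collects baseline data before the allocation is accessible.

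The reply does not remove the mismatch between an imbalance criterion and an efficiency aim, or the absence of a list and threshold.

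**Conclusion.** The point holds in a limited form. For SBP, the imbalance rule adds almost nothing to the reported precision already obtained from baseline SBP. A fixed prognostic list would add about 1 to 3 points of power if it explains 10-20% of residual variance, and at most about one point at 2-5%. These figures assume 240 per arm analysed, an SD of about 17 mmHg, a baseline-to-change correlation of 0.3 to 0.5, and a p<0.10 definition of imbalance; none of the last three is in the documents.

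Applied mechanically, the rule does not inflate type I error and can be slightly conservative. The remaining weakness, for both SBP and PAM, is that the model is settled only after the arms are compared, which leaves room for selective choice. For PAM that is the only objection. The change is worth making because it is cheap, not because the loss is large.

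**What to change.** In both documents, delete imbalance as a criterion. Before outcome data by arm are seen, fix a short list of covariates measured before randomisation and included whatever their balance:

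- **SBP model:** arm, baseline SBP, age, gender, race/ethnicity, plus BMI if a pre-randomisation value is available in the health record. The Protocol mentions BMI only as an example of record data and does not give its timing.
- **PAM model:** arm, baseline PAM, age, gender, race/ethnicity, baseline self-rated health (SF-1).

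A model that adds imbalanced baseline covariates may be shown only as a labelled sensitivity analysis.

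The cost is a wording change, a few degrees of freedom out of about 480, and some handling of missing covariates, for which the plan already allows multiple imputation. No extra participants or survey items are needed.

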Our primary outcome will be a 5mmHg change in systolic blood pressure from baseline to study end at 6 months. We will conduct an intent-to-treat analysis. We will use paired t-tests to compare the mean difference in SBP between the intervention and control groups. We will also conduct a multiple linear regression analysis for change in SBP adjusting for covariates which may be imbalanced even after randomization to improve efficiency of our estimates. We will also adjust for baseline SBP. The distribution of change in SBP will be assessed and if it is non-normal (skewed) we will use an appropriate transformation (such as natural log) or we will use a generalized linear model with appropriate family and link choices to model our outcome. For the secondary outcome measure, we will use paired t-test for pre-post differences of PAM scores. A multiple linear regression model will also be used to account for additional imbalances in demographic and baseline health characteristics not evenly distributed by arm. In all models, a binary indicator for control/intervention group will be included. Baseline PAM score will also be adjusted for in the model. Covariates with missing data will be assessed for patterns of missingness and non-ignorability and will be multiply imputed if deemed necessary and reasonable.

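### If change in SBP is skewed, the plan names a log that a signed change does not allow, or a GLM left open, with no requirement to report in mmHg; the switch is not needed.

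*SAP*

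**What the plan says.** The SAP puts the outcome in mmHg: "Our primary outcome will be a 5mmHg change in systolic blood pressure from baseline to study end at 6 months". The Protocol's Sample size paragraph uses the same scale, sizing the trial to "detect a 5mmHg difference in systolic blood pressure at 90% power and type I error of 0.05".

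The SAP then lists an unadjusted comparison of the two groups and, in addition, a linear regression of the change, for which it says "We will also adjust for baseline SBP". A conditional step follows. The Protocol's Data analysis text reads "The distribution of change in SBP will be assessed and if it is non-normal (skewed) we will use an appropriate transformation (such as natural log", and the SAP repeats it: "if it is non-normal (skewed) we will use an appropriate transformation (such as natural log) or we will use a generalized linear model". The second route is "a generalized linear model with appropriate family and link choices to model our outcome".

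Neither document gives a criterion for skewness, a rule for changes at or below zero, a constant to add before taking logs, a family or link, a way to choose between the two routes, or a way to bring the result back to mmHg.

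**The concern.** The variable that triggers the switch is a difference between two readings, so it can be negative, zero or positive. The only transformation named cannot be computed for part of that range. A direct log could therefore not include everyone, although the SAP commits to intent-to-treat. A log after adding a constant can include everyone, but its result is a ratio that moves with the constant. A gamma GLM of the change also needs positive values.

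The adjusted result could then be one that cannot be set against the 5 mmHg on which the trial is sized, with the route and any constant chosen after the distribution has been seen.

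**Working it through.** **Inputs.** From the documents: 5 mmHg, 90% power, type I error 0.05 (taken as two-sided), 240 per arm, 35% loss. Not in the documents, so assumed: SD, mean changes, skewness.

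**1. The plan's own sample size, solved for SD.** SD = 5 × √(n/2) / (1.960 + 1.282).
- n = 240: 5 × 10.954 / 3.242 = 16.9.
- n = 156 (65% of 240, if the 240 are enrolled and 35% are then lost): 5 × 8.832 / 3.242 = 13.6.

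The noncentral t gives 16.86 and 13.58, which are used below.

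**2. Share with an undefined log.** P(change ≤ 0) = F(−mean/SD), where F is a standardised gamma with the stated skewness; arms averaged. Control mean 0, intervention mean −5. Worked case, skewness 2, SD 13.58: control 1 − e^(−1) = 0.632; intervention 1 − e^(−(1 + 5/13.58)) = 0.745; average 0.689.

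| Skewness | SD 13.58 | SD 16.86 |
|---|---|---|
| −2 | 0.450 | 0.431 |
| −1 | 0.511 | 0.495 |
| 1 | 0.631 | 0.620 |
| 2 | 0.689 | 0.679 |

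That is 43-69%. Coded as a reduction, the shares are one minus these: 31-57%. If both arms also fall by a further 5-10 mmHg, the shares are 58-88% coded as change and 12-42% coded as reduction.

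**3. Log after adding a constant.** Each change is shifted so that the sample minimum becomes 1, 10 or 50, with the long tail on the right. Ratio = exp(difference in mean logs). True effect: 5 mmHg throughout.

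| SD, skewness | min = 1 | min = 10 | min = 50 |
|---|---|---|---|
| 13.58, 1 | 0.764 | 0.849 | 0.934 |
| 13.58, 2 | 0.591 | 0.791 | 0.925 |
| 16.86, 1 | 0.804 | 0.868 | 0.938 |
| 16.86, 2 | 0.628 | 0.805 | 0.928 |

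Type I error stays near 5% (4.5-4.9%) and power is 94-100%. The verdict at 0.05 differs across the three constants in about 2-5% of simulated trials.

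**4. GLM routes.**
- Gaussian family, identity link, on change: the linear regression again, in mmHg.
- Gamma family on change: needs positive values.
- Gaussian family, log link, outcome coded as reduction: the coefficient is a ratio of mean reductions, but predicted arm means can be subtracted to give mmHg. With mean reductions of 5 and 10 it recovered the arm means in every run. With mean reductions of 0 and 5, an arm's sample mean was at or below zero in 46-57% of runs and those arm means could not be fitted.
- Gamma family on 6-month SBP, adjusted for baseline: with an assumed baseline of 148 (SD 15) and skewness 1.5, the identity link gave −5.1 mmHg, and the log link with standardised predictions gave −5.2 mmHg.

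**5. Staying in mmHg under the same skewness.** The two-sample t-test on change has 89-91% power and 4.8-5.2% type I error. Regression on arm and baseline with robust (HC3) standard errors has 92-98% power and 4.1-5.5% type I error, for a baseline to 6-month correlation of 0.3-0.7. The t-test's 90% is built in, because each SD was solved for it. At SD 16.9 with 156 per arm, power is 74% by formula and 74-75% by simulation at skewness 0 to about 4. The result is that skewness costs almost nothing, not that the trial has 90% power.

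**The case against.** The strongest reply is that the text is permissive. The log is an example of an appropriate transformation, and one that is undefined for much of the sample is not appropriate. This stands in part: the plan does not commit to an impossible step. But the only example it gives does not suit the variable it names, and nothing else is specified.

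Second, a GLM need not leave the mmHg scale. This stands. A reader might infer that every GLM route ends in a ratio; the routes above show otherwise, and the SAP wording can be read to allow a model of 6-month SBP, which is positive. What remains is that the plan does not require a mmHg result.

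Third, the switch is conditional and, on the natural reading, applies to the additional regression, so the unadjusted comparison still gives mmHg. This also stands, and it limits the damage. With no criterion stated, though, the switch could fire often: a 5% skewness test fired in every simulated trial at absolute skewness 1 or 2.

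Fourth, the inferential harm is small. A shifted log keeps its type I error and gains power. True, but for a different estimand.

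A reader might also infer that participants with undefined values would be excluded, which in simulation would leave 5-10% power. The documents plan no such exclusion, so that figure is no measure of this plan's loss.

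**Conclusion.** The point holds as a should-fix on scale and specification. The named log cannot be computed for about 43-69% of participants under the main assumptions (12-88% across other means and codings). A shifted log reports the same 5 mmHg effect as anything from 0.59 to 0.94, depending on SD, skewness and constant. The GLM route may or may not return mmHg.

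The documents do not support reading this as a loss of every mmHg result or as inflated type I error. The unadjusted between-group comparison stays in mmHg, and the verdict moves with the constant in only about 2-5% of trials.

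The undefined log is certain whenever a change is at or below zero. The sizes rest on assumed SD, means and gamma skewness, with the same shape in both arms. The finding that the switch is not needed rests on simulation at 156-240 per arm with a two-sample test. The SAP calls its test paired, which is a separate matter.

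**What to change.** In both the SAP and the Protocol's Data analysis text:
- Delete the log/GLM switch for change in SBP.
- Keep the planned linear regression of change (or 6-month SBP) on arm and baseline SBP, in mmHg, with robust standard errors whatever the skewness.
- Make any log or GLM analysis a sensitivity analysis based on SBP itself, which is positive, and report it back as a mmHg difference.

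The cost is a few sentences in two documents, with no new data and no material loss of power for the mmHg comparison. If outcome data have already been seen, date and disclose the change. Which analysis is primary and which other covariates enter the model are separate questions that this change leaves alone.
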